Undernutrition is a common problem in patients with cystic fibrosis (CF) despite international consensus that the patients shall be given 120-200% of energy recommendations. Studies imply that one problem might be that the patients are not compensated for the essential fatty acid deficiency (linoleic acid, LA), which is well known in these patients. This deficiency is shown not to be due to fat malabsorption, but associated to an increased turnover of arachidonic acid, a transformation product of LA. This abnormality is related to mutations associated with a more severe clinical phenotype. The most common and typical symptom of LA deficiency is poor growth. Studies in animals have further indicated that many of the symptoms in CF are related to the deficiency. A series of recent prospective studies from Wisconsin corroborate the importance of LA for growth. In Sweden LA has been supplemented to most patients since the late 70', and the condition of patients have been among the leading in the world regarding growth, pulmonary function and survival. Short-term studies have shown better effect of LA supplementation compared to similar supply of energy without including extra LA. There are few long-term studies, performed before the gene was identified, giving very heterogeneous patient groups in regard to genotype, but some positive results on growth and physiology. It's of interest that modern personalized extremely expensive therapy with correctors and potentiators for Cystic Fibrosis Transmembrane Conductance Regulator may influence lipid metabolism. LA might thus tentatively be a cheap adjuvant to this modern therapy, but this has to be specially studied.

The benefit for the patients would be great if the expected positive effect can be proved in the planned study. ***The treatment will be cheap and without adverse effects.*** From socioeconomic point of view is would be a great advantage.

AIM

To investigate the impact of long-term supplementation of fatty acids on clinical status and metabolism in patients with cystic fibrosis (CF).

DESIGN

A double-blind controlled randomized study of supplementation of linoleic acid (LA) compared to oleic acid (OA), and with long-chain omega 3 fatty acid (DHA) for one year to patients with CF.

BACKGROUND

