The cause of the low DHA is not clear, but the improvement of DHA by LA supplementation suggests that it might not be of primary importance (Farrell et al 1985, Strandvik et al 2001) and maybe associated with a high phospholipid turn-over (Bhura-Bandali et al. 2000, Strandvik 2010, Rogiers et al 1984). However, long-term studies in CF mice and a recent paper suggest that the ratio between AA/DHA in blood cell tissues is related to the liver disease in CF, suggesting that the concentrations of polyunsaturated fatty acids (PUFA) might contribute to the unexplained liver affection in many of the patients (Lindblad et al. 1999; Beharry et al. 2007; van Biervliet et al 2010; Jørgensen et al. 2012, Drzymala-Cryz et al, 2017). Because one study of transgenic CF mice showed low DHA associated with morphological changes in ileum and pancreas (Freedman et al 1999), although later not confirmed in a long-time study (Beharry et al 2007), many clinical trials with supplementation of omega-3 LCPUFA started, but mainly failed to show clinical improvement despite marked increase of omega-3 fatty acids in plasma (van Biervliet et al. 2008, Oliver et al. 2011, Alicandro et al. 2013). One study with regular intravenous supplementation of omega-3 for 3 months even showed negative impact on the patients (Durieu et al. 2007). As mentioned above one study showed

marked clinical improvement by a combination of omega-3 and omega-6 supplementation (Oliveira et al. 2010).

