progression of the pulmonary damage. Furthermore many studies have shown that OA increases compensatory when LA decreases (Christophe et al 1994), and it was shown in Toronto, (contributing to their persistent use of high fat diet when rest of the world prescribed low fat diet to CF) that high OA stimulated the growth of *Staphylococcus aureus*, the first colonizer of the airways in patients with CF (Campbell et al.1983). Similar imbalance of LA and OA was also found to impair the oxygen pressure influencing the hemoglobin oxygenation which would be a factor increasing the airway pathology in CF (Campbell et al 1976). Thus, it seems important to increase LA concentration and reduce AA concentration in the patients with CF also from reported pulmonary associations (Wheelock & Strandvik 2020). Many studies have shown that the pulmonary symptoms are the most affected persistent problem in the neonatally screened patients despite their high caloric diet, and improved early growth is associated with better pulmonary function up to 12 years of age (Sanders et al 2018).

It is also important that the hyperactivity of the epithelial sodium channel (ENaC), which is shown to contribute to the pulmonary symptoms, seem to be normalized by LA supplementation, as notified in sweat glands and kidneys (Strandvik 2021), and which might be an effect of the protein-lipid interaction. In recent studies the interaction of modulators and phospholipids have been shown (Liessi et al.2020; Kopp et al.2018 .

The recent discovery of the importance of the long-chain PUFA of the omega-3 series for the normal inflammatory response by transformation to prosolving specialized markers (SPM), the anti- inflammatory lipoxines (Rogeiero et al. 2012)

may indicate that supply of omega-3 fatty acids might be important as a general treatment for CF patients with their chronic airway inflammation. Further improvement might therefore be expected with a combined supplementation, especially since the long-chain omega-3 fatty acids inhibit delta-6 desaturase and thereby may further reduce the transformation of LA to AA (Hagve et al 1988).

WORKING PLAN

Patients and Eligibility.

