Sampling. Mixture in local laboratory with freezing of an aliquote for later transport to Poznan

6. *Metabolic tests*

- Urine sample for 8-isoprostanate and lipid mediators as eicosanoids, docosanoids and linoleic acid metabolites (directly to freezer -80 each sample in 2 x 8 ml and in 4 x 2 ml) for later analyses in Stockholm.
- Indirect calorimetry at start and after 12 months (if available in the hospital).
- Sweat test at start and after 12 months. **Both sodium** and chloride analyses.
- Oral glucose tolerance test.

7. *Quality of life.*

Quality of life will be assessed through the CF Questionnaire Revised (CFQ), a disease-specific tool that measures health-related quality of life in patients with

CF. There are different versions of the questionnaire: two for children over 6 years, one to be completed by the child and one to be completed by parent (CFQ Child and CFQ-Parent, respectively).

8. Compliance with the treatment

Compliance with the treatment will be evaluated by monthly contact with the study coordinator of respective centre, when not used vials will be registered and new supplied. The patients are asked to make a dairy over the daily intake also reported monthly to the coordinator. Extent of physical activity shall be notified.

9. Statistics

All data will be collected in identical Excel files and analysed in one center at end study.

The main analysis will be carried out on the intention-to-treat population defined as all randomized patients. We will also conduct a secondary analysis on the per-protocol population excluding patients not receiving the allocated treatment for more than 2 months.

Between-treatment differences in the primary outcome across time points will be evaluated by fitting random intercept linear mixed-effects models. Mixed effects model can account for intra-correlated repeated measures on the same subjects and accommodate missing data due to dropouts. The models will include the z-score of BMI as response variable, treatment, time and time x treatment interaction as independent variables. The model coefficients for the time x treatment interaction will be considered an estimate of the treatment effect on changes in the study outcome. Time will be included in the model as categorical variable with the following categories: baseline (pre-treatment), +6 months and +12 months from treatment allocation.

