Secondary and explanatory outcomes will be compared across treatment groups using the paired t-test for normally distributed variables, otherwise the non-parametric Wilcoxon signed-rank test for dependent samples will be used.

A stratified analysis by sex will be performed.

RISK-BENEFIT

There will be no adverse effects to expect of this treatment , since the control group will have the same treatment as offered generally to patients, i.e. extra calories. The extra LA will not exceed the general intake in US (Choque et al 2014). Both groups get similar amount of omega-3 fatty acids; dose in agreement with general recommendations. The extra burden of investigations is small since the patients always have more extensive investigations at the yearly checkup.

IMPORTANCE

If clinical status is improved the patients in both groups will be asked for the possibility to continue with Group A therapy for one further year (requires new ethical applications). Furthermore, good result would indicate a multicenter study for treatment from diagnosis in countries with neonatal screening, which would be extremely important since many of the symptoms start early and especially the supply of high caloric diet gives many problems in patients and parents, and unsatisfying results, It can also have the potential to be a cheap complement to modern expensive drug treatment.

A special benefit for individuals and society would be if this simple, cheap and non hazardous treatment can reduce the enormous costs of the modern drug treatment, which is further not always available.

References:

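### The protocol rules out adverse effects in advance but describes no adverse-event or tolerability recording, no reasons for withdrawal and no safety analysis, so that statement cannot be supported

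*Protocol*

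**What the plan says.** The assertion is made twice. The opening summary says "The treatment will be cheap and without adverse effects", and RISK-BENEFIT says "There will be no adverse effects to expect of this treatment".

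RISK-BENEFIT gives as its main reason "since the control group will have the same treatment as offered generally to patients, i.e. extra calories". That concerns the oleic acid (OA) arm. For the linoleic acid (LA) arm the only specific argument is a dietary comparison: "The extra LA will not exceed the general intake in US". The docosahexaenoic acid (DHA) dose, the same in both arms, is said to agree with general recommendations.

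On data collection:
- Table 1 has no adverse-event row.
- Section 8 says "Compliance with the treatment will be evaluated by monthly contact with the study coordinator of respective centre". The content described is unused vials, an intake diary and physical activity.
- Section 9 of the Protocol, repeated in the SAP, defines an intention-to-treat and a per-protocol population. It has no safety population and no safety analysis.
- Sample size expects close to 10% withdrawal. No recording of the reasons is described.

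**The concern.** A statement that a treatment has no adverse effects is an empirical claim. This plan makes the claim before the data and describes no means of testing it for clinical events. The children are aged 5 to 15, selected for severe mutations with pancreatic insufficiency, and take a daily fat emulsion for a year. The protocol itself expects that extra enzymes may be needed, so digestive tolerance is an obvious thing to ask about.

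What is at stake is information that cannot be rebuilt later. A child who stops because of intolerance would appear only as missing data or as a per-protocol exclusion. IMPORTANCE foresees a further year of LA treatment under new ethical applications, and a later study starting at diagnosis. As the plan is described, those applications would have no adverse-event rates from this trial to draw on.

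**Working it through.** **Step 1. Denominator.** The safety claim rests on no stated figure, so the only inputs are the sample sizes. The plan's figure is 42 per group for a difference of 0.5, SD 0.8, two-sided alpha 0.05 and 80% power. The normal formula gives 2 × (1.960 + 0.842)² × (0.8/0.5)² = 40.2, rounded up to 41. The t-based solution is 41.2, rounded up to 42, so 84 in total reproduces. Planned enrolment is 90, or 45 per group.

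**Step 2. What is collected that could show harm.**

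| Measure | Place in Protocol | Limit as a safety measure |
|---|---|---|
| Exacerbations, antibiotics | Patients and Eligibility; secondary outcome | Treated as efficacy, compared with the year before |
| FEV1, oxygen saturation | Secondary outcomes; section 3 | Treated as efficacy |
| Blood count, liver, renal, lipids, CRP | Section 4 | Routine panel at start and end in the text, although Table 1 has a blood sample at 6 months |
| Lipid mediators, cytokines, 8-isoprostane | Explanatory outcomes | Not designated as safety data |
| Calprotectin, fat absorption | Section 5 | Not done in all patients |
| CF questionnaire | Section 7; Table 1 | Not in the outcome list; child and parent versions described for over 6 years only |
| Enzyme increases, unused vials | Patients and Eligibility; section 8 | Indirect signs of intolerance; no reason recorded |

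For secondary and explanatory outcomes, section 9 names paired tests to compare the arms. Those suit change within a child, not two independent groups. Because both arms receive the same DHA dose, a DHA effect cannot be isolated by comparing them.

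**Step 3. What the continuous markers could show.** With a valid two-sample comparison, the difference detectable with 80% power is (1.960 + 0.842) × √(2/n). This is 0.59 SD at n = 45 and 0.61 SD at n = 42, in either direction.

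**Step 4. What recorded events could show.** With zero events in n children, the upper limit for the true risk is 1 − 0.05^(1/n) (one-sided 95%) or 1 − 0.025^(1/n) (exact two-sided 95%).
- n = 45: 6.4% and 7.9%
- n = 42: 6.9% and 8.4%
- n = 90, arms pooled: 3.3% and 4.0%

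The chance of at least one event in 45 children is 1 − (1 − p)^45:
- p = 1%: 36%
- p = 2%: 60%
- p = 5%: 90%
- p = 10%: 99%

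**Step 5. Power to separate the arms on an event rate.** The documents give no rates, so these are assumed, with 45 per arm and two-sided 5%:
- 5% against 10%: 14%
- 10% against 20%: 26%
- 10% against 30%: 67%
- 10% against 35%: 82%

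Adverse-event data from this trial would therefore be descriptive. They would reveal common problems and bound the rest, but would not establish absence of harm.

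**The case against.** The strongest reply is that the plan measures a great deal that bears on harm, as Step 2 shows. That stands. A reader might infer that the trial cannot detect harm at all. The documents do not support this: a shift of about 0.6 SD in a liver enzyme or CRP is within reach of a proper two-group comparison, and infections are registered. The choice of paired tests is a separate defect of analysis, not an absence of data. What remains is that none of these measures asks about intolerance or picks up an unforeseen event.

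A reader might also infer that the BACKGROUND contradicts the claim of no adverse effects. It does not go that far.
- Omega-3: "One study with regular intravenous supplementation of omega-3 for 3 months even showed negative impact on the patients". That was intravenous, and its reference title calls it an open pilot observational study. Here DHA is given by mouth.
- Oleic acid: the text reports "that high OA stimulated the growth of" *S. aureus*, but the reference title describes in-vitro work. The oxygenation remark concerns an imbalance of LA and OA, not an OA supplement.
- Linoleic acid: the reluctance of many centres is reported in order to be answered. The same section cites a fall in arachidonic acid with LA, no rise in inflammatory markers in healthy people, and lower prostaglandin F2α in CF patients.

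These show documented uncertainty, not harm.

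Finally, IMPORTANCE speaks of "this simple, cheap and non hazardous treatment can reduce the enormous costs of the modern drug treatment", and a reader might take safety to be a planned conclusion that licenses further use. It is a premise in a conditional sentence. Continuation depends on improved clinical status and needs new ethical applications.

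It is also fair to say that zero-event limits apply to any trial of this size. They do not measure the defect. They show how far a safety statement could go once events are recorded.

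**Conclusion.** The point holds in this form: no systematic adverse-event or tolerability recording, no reasons for withdrawal and no safety analysis are described, and the collected markers are not designated as safety data. Tolerability and unexpected clinical harms cannot be assessed, and the statement of no adverse effects cannot be supported. The stated reason covers mainly the control arm, with only a comparison to US intake for LA.

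With recording in place, 45 per arm would show a 5% event at least once with 90% probability. An event type never seen would still be compatible with a true risk of up to 6.4% (one-sided) or 7.9% (exact two-sided). This assumes that all 45 children per arm take the supplement and are asked.

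The finding does not affect the primary analysis. The opening pages of both documents were not part of the text examined, so the conclusion is that nothing is described in the text available. The change is worth making before data collection, since the data cannot be recovered afterwards.

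**What to change.** 1. **Collection.** Add a short fixed set of adverse-event and gastrointestinal-symptom questions to the existing monthly contact, identical in both arms and at all centres, with the reason for stopping where a child stops. Add an adverse-event row to Table 1 at 6 and 12 months.
2. **Analysis.** Add to section 9 the number and percentage of children with any event, any serious event and withdrawal because of an event, by arm, with exact 95% confidence intervals, in all children who took at least one vial. Report the liver, lipid and CRP tests and the exacerbations as safety data too, compared by a method for two independent groups.
3. **Wording.** Replace both statements of no adverse effects with one that fits the design. For example: adverse events will be recorded in both arms, and an event type not seen in 45 children remains compatible with a true risk of up to 7.9% (exact two-sided 95% limit).

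Cost: at most 90 × 12 = 1,080 brief monthly records, simple definitions of an event and of seriousness, some coordinator time, one extra table and a more cautious safety statement. No change to dose or treatment rules is proposed.

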## 9. Statistics

All data will be collected in identical Excel files and analysed in one center at end study.

The main analysis will be carried out on the intention-to-treat population defined as all randomized patients. We will also conduct a secondary analysis on the per-protocol population excluding patients not receiving the allocated treatment for more than 2 months.

Between-treatment differences in the primary outcome across time points will be evaluated by fitting random intercept linear mixed-effects models. Mixed effects model can account for intra-correlated repeated measures on the same subjects and accommodate missing data due to dropouts. The models will include the z-score of BMI as response variable, treatment, time and time x treatment interaction as independent variables. The model coefficients for the time x treatment interaction will be considered an estimate of the treatment effect on changes in the study outcome. Time will be included in the model as categorical variable with the following categories: baseline (pre-treatment), +6 months and +12 months from treatment allocation.

Secondary and explanatory outcomes will be compared across treatment groups using the paired t-test for normally distributed variables, otherwise the non-parametric Wilcoxon signed-rank test for dependent samples will be used.

A stratified analysis by sex will be performed.

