Patients with CF, carrying 2 severe mutations referred to Class I and II, i.e. mutations associated with more severe LA deficiency and more severe clinical symptoms, (like delF508, 394delTT) are included after informed consent. The reason for including only those with clinically more severe phenotype is that those have pancreatic insufficiency and also other symptoms more expressively related to genotype (see above). Exclusion criteria will be pregnancy and transplantation and age above 15 and below 5 years (due to pulmonary function tests) and severe liver disease (cirrhosis, portal hypertension). The patients shall not have taken any lipid supplements for 2 months before inclusion and not be treated with any modulators (like Orkambi, Trikafta).

The patients will keep to their ordinary treatment of PERT and vitamins and that for the pulmonary symptoms and infections. No special dietary recommendations will be given, but PERT might be increased, when the supplement is given and that shall be registered. Number of pulmonary exacerbations and type of treatment, including antibiotics, are registered and also compared with the year before the study.

Sample size

A sample of 84 patients (42 per group) will ensure that a two-sided test with α =0.05 has 80% power to detect a 0.5 mean difference in 1-year change in weight-

for-age Z-score, assuming a pooled standard deviation of 0.8. This last figure has been obtained from a previous intervention study on cystic fibrosis patients (Alicandro et al. 2013). Since we expect a withdrawal rate of close to 10%, we planned to enroll 90 patients (45 per groups). The patients and caregivers will be informed by oral and written information and included after informed consent. The study is approved by local Ethic Committees and by the one at Karolinska Institutet and the study is performed according to the Helsinki Declaration.

Design

The study is designed as a double-blind randomized clinical trial

The patients will be randomized to either

- treatment A: linoleic acid (12 g for children 5-15 years) + 600 mg algeal DHA
- treatment B: oleic acid (12 g for children 5-15 years) + 600 mg algeal DHA

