The fatty acids will be given daily for 12 months, in vials containing an emulsion of totally 20 ml (provided by AKK Company, Karlshamn, Sweden and Copenhagen Denmark, packed by WinterMedic, Odense, Denmark), which can be mixed with milk, juice, sour cream, porridge or any similar feeding at breakfast time. Some extra enzymes may be added.

The treatment will last 12 months, starting and ending at time of the yearly check up of the patients. Half the number of patients will be randomly allocated to receive either treatment A or B. An independent researcher (not involved in the study) will generate the allocation sequence at each center. This will reduce small differences in local treatment policy. The vials with supplementation will only be coded (black or white capsula) so neither patient nor caregivers or staff in charge will be informed by the type of supplementation.

Primary Outcome

- BMI Z-score, weight-Z-score

Secondary outcomes

- Height Z-score
- FEV1 (% of predicted) and oxygen saturation
- Exacerbations and infectious parameters compared to year before.
- Plasma phospholipid fatty acid profile.
- Plasma concentration of IGF-I

Explanatory outcomes

- Bone mineral density
- Lean body mass and fat mass.
- Liver function tests
- Lipid mediators (like eicosanoids and docosanoids)
- Cytokines
- 8-iso-prostane
- Sweat sodium and chloride concentrations
- Renal sodium excretion
- Resting energy expenditure
- Intestinal function (fecal calprotectin and fat absorption coefficient)
- Oral glucose tolerance with insulin determination.

METHODS

Patients will be screened for enrollment and will be allocated to one of the treatment at baseline visit. Follow-up visits will be scheduled at 6 and 12 months after treatment allocation. Some measures, like fat absorption coefficient and calprotectin and resting energy expenditure, exhaled NO and ergometer test will not be performed in all patients due to limited capacity at some centres. The study procedures are summarized in table 1.

Table 1. Outline of study procedures

	Baseline visit: Screening and allocation	+6 months	+12 months
Anthropometry	X	X	X
DXA	X		X
FFQ	X	X	X
24-h dietary recall	X	X	X
Pulmonary function	X		X
Blood sample	X	X	X
F-Calprotectin	X		X
Urine sample	X		X
Ergometer test with oxygen saturation	X		X
Oral glucose tolerance	X		X
Indirect calorimetry	X		X
Sweat test	X		X
Compliance to treatment	X	X	X
CF Questionnaire	X	X	X

1. *Anthropometry.*

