Height and weight are controlled with the same equipment for each patient at respective centre and at each scheduled visit (baseline, 6 and 12 months after allocation). Z-scores of weight, height and BMI will be computed using WHO as growth standard. DXA is performed at start and after 12 months period for determination of bone mineral content and density, lean body mass and fat mass.

1. *Food registration.*

- Food frequency questionnaire (FFQ) will be performed at start and each scheduled visit, mainly used for calculation of energy intake and intake of fat and fatty acids (validated questionnaire Eriksson S et al. 2010). Since the products are different in different countries the FFQ form can only suggest **type** of products to be evaluated, complemented by the local dietician. The reason to include these registrations is to individually make a comparison with intake at start and end of study possible, checking that not major changes have occurred in diet, which can influence the results.
- 24-hour recall will be performed at start, 6 months and 12 months after allocation as a complement to FFQ for portion size, type of products etc.

3. *Pulmonary function.*

- Routine pulmonary function (FEV1) at each clinical visit
- Full spirometry at start and end of treatment
- Exhaled NO (if available)
- Ergometer test at start and end
- Oxygen saturation (ear-tip).

4. *Biochemistry.*

- Routine blood biochemistry (fasting) at start and end of treatment period, including Hb, platelets, white blood cell count and differential count, ASAT, ALAT, alkaline phosphatase, GGT, PK, total and conjugated bilirubin, bile acids, cholesterol, lipoproteins, triglycerides, urea, creatinine, glomerulus filtration rate. Ig-G, CRP, sedimentation rate.

- 1 ml serum/plasma for later analyses (to freezer divided in 4 tubes for later analyses of lipid mediators at KI).
- 0,5 ml for IGF-I analysis (to freezer for later analysis in Sweden)
- 0.5 ml plasma for cytokines (to freezer for sending to Stockholm for analyses (OLINK, Uppsala, Sweden).
- 0.5 ml plasma for analyses of phospholipid fatty acids (to freezer for later analysis in Poznan or Stockholm).
- Urine sample for routine tests, incl sodium and creatinine concentrations.

5. *Intestinal function*

- F-Calprotectin at start and after 12 months (in freezer for later analyses at one center)
- Fat absorption at start and 12 months. Three day dietary recording and feces

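### The trial is sized on weight-for-age Z-score, but the only primary model written out analyses BMI Z-score, and the plan does not say which one decides.

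*SAP*

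**What the plan says.** **Sample size (Protocol, Sample size).** The trial is planned to have "80% power to detect a 0.5 mean difference in 1-year change in weight"; the phrase continues to weight-for-age Z-score. The test is two-sided at 0.05, "assuming a pooled standard deviation of 0.8". This gives 84 patients, 42 per group, with 90 to be enrolled. No difference or SD is given for BMI Z-score.

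**Primary outcome (Protocol, Primary Outcome).** The whole entry is "BMI Z-score, weight-Z-score". It gives no order, no co-primary rule and no time point.

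**Derivation (Protocol, Methods, Anthropometry).** The two are separate variables: "Z-scores of weight, height and BMI will be computed using WHO as growth standard".

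**Analysis (SAP 9. Statistics; the same text is in Protocol 9. Statistics).** "Between-treatment differences in the primary outcome across time points will be evaluated by fitting random intercept linear mixed-effects models". The response is then named: "The models will include the z-score of BMI as response variable, treatment, time and time x treatment interaction as independent variables". On the estimate: "The model coefficients for the time x treatment interaction will be considered an estimate of the treatment effect on changes in the study outcome". On time: "Time will be included in the model as categorical variable with the following categories: baseline (pre-treatment), +6 months and +12 months".

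**The concern.** The variable with a sample size has no written model, and the variable with a written model has no sample size. The list of primary outcomes fits either place and so does not settle the matter.

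What is at stake is the decision rule. If BMI Z and weight Z disagree at 12 months, the plan does not say whether the trial succeeded. A choice made after unblinding could not be shown to have been planned.

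There is a smaller gap of the same kind. Time with three levels produces two time-by-treatment coefficients, one at 6 months and one at 12 months, and neither is named as the deciding test.

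**Working it through.** **1. Reproduce the plan's figure for weight Z.** Inputs from Protocol, Sample size: difference δ = 0.5, SD of change σ = 0.8, n = 42 per group, two-sided α = 0.05. For a two-sample t-test on change:

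- Noncentrality = δ / (σ√(2/n)) = 0.5 / (0.8 × √(2/42)) = 2.864, with 2n − 2 = 82 df.
- Power from the noncentral t is 80.8% at 42 per group and 79.8% at 41.

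So 42 is the smallest group size that reaches 80%. The calculation is right for the variable it names.

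**2. Try to carry it over to BMI Z.** The same formula needs a BMI Z difference and SD of change, and the documents give neither. The values below are assumptions, at 42 per group.

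| Assumed SD (difference 0.5) | Power |
|---|---|
| 0.6 | 97% |
| 0.7 | 90% |
| 0.8 | 81% |
| 0.9 | 71% |
| 1.0 | 62% |

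| Assumed difference (SD 0.8) | Power |
|---|---|
| 0.3 | 40% |
| 0.4 | 62% |
| 0.5 | 81% |
| 0.6 | 92% |

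The standardised difference detectable with 80% power at 42 per group is 0.6186. For a difference of 0.5, the break-even SD is 0.5 / 0.6186 = 0.81. The stated power transfers to BMI Z only if its difference-to-SD ratio is at least about 0.62.

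**3. Check whether the model, rather than the response, changes the power.** With a random intercept and complete data, the 12-month coefficient is tested on 164 df. If compound symmetry is true, power at δ = 0.5 and σ = 0.8 is 81.3%. The type of model is not the problem; the response variable is.

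**4. The two coefficients.** Null simulation: random-intercept fit, complete data, 42 per group, three visits, 200,000 trials per case. Under compound symmetry the two coefficients correlate 0.5. The false-positive rate is 5.0% (0.0496) if the 12-month coefficient alone decides and about 9% (0.0893) if either one counted as success.

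**5. Dependence on the covariance.** The documents give no variances or correlations by visit, so two alternatives were assumed. The random-intercept fit estimates the variance of a change by averaging over the three pairs of visits.

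- *Random walk* (variance of change doubles from 6 to 12 months). The pairwise variances are in the ratio 1 : 2 : 1, with average 4/3. The true 12-month variance is 2, so the ratio of estimated to true is 0.667. The error rate is 2Φ(−1.96√0.667) ≈ 0.110; simulation gave 0.109.
- *Equal change variances, correlation 0.70.* The pairwise variances are 1, 1 and 2(1 − 0.70) = 0.6, with average 0.867. The error rate is 2Φ(−1.96√0.867) = 0.068; simulation gave 0.068.

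When the 12-month change is tested with its own variance (82 df), the rate is 0.0496, 0.0501 and 0.0501 in the three cases. With complete data this equals the unstructured-covariance contrast.

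**The case against.** The power statement is correct for the variable it names, weight Z is one of the listed primaries, and the protocol makes no explicit power claim for BMI Z. The Statistics section speaks of a single primary outcome and then names BMI Z, so a natural reading is that BMI Z is analysed and weight Z served only for sizing. The plural "models" might also be meant to cover weight Z.

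These readings are possible, but they compete and the text chooses none of them. On the first, the analysed primary has no power basis. On the second, there are two unranked primaries and no decision rule. The endpoint is unsettled either way.

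Other parts of the objection stand. No power deficit is shown: the ranges rest on assumed inputs and straddle 80%. They also use 42 per group, whereas 45 are to be enrolled and the mixed model uses partial data. At 45, an upper bound, SD 0.9 gives 74% instead of 71%, and the break-even SD is 0.84 instead of 0.81. The 9% concerns the two time points, not the two endpoints, and it depends on a success rule that the plan neither states nor excludes. The sizing on one-year change already points to the 12-month coefficient. The covariance results come from assumed structures with complete data and were not checked under the expected withdrawal of close to 10%. None of this removes the mismatch.

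**Conclusion.** The concern holds with high confidence and must be fixed before unblinding. Its weight rests on one fact that can be read directly from the documents: the sample size and the only written primary model use different variables, and no rule says which decides.

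The numerical consequences are less certain. Power for BMI Z cannot be determined from the documents and may lie above or below 80%. The inflation to about 9% is conditional on counting either coefficient as success. The 5.0% for the 12-month coefficient alone holds under compound symmetry, and rose to 6.8% and 10.9% in the two other covariances assumed.

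**What to change.** Name one primary endpoint and make its 12-month time-by-treatment coefficient the single deciding test at two-sided 0.05. Label the 6-month coefficient supportive and the other endpoint secondary; testing the two endpoints in a fixed sequence is one option. Then choose between:

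- **(a) Weight-for-age Z as the response.** This matches the existing sample size and needs only wording.
- **(b) BMI Z as the response.** The sample-size paragraph and its power must then be restated with a justified BMI Z difference and SD, which could change the number of patients.

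Align the Sample size, Primary Outcome and Statistics sections of the protocol, and section 9 of the SAP, with that choice.

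The cost is that the endpoint not chosen loses equal primary status. Under (a) that is BMI Z, the only response the current model names.

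Optionally, if the 5% level is to hold beyond compound symmetry, fit the three visits with an unstructured covariance. If compound symmetry is in fact true, this costs about 81.3 − 80.8 = 0.5 percentage points of power at the sized inputs with complete data.
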